9.14 Routine Adverse Event Reporting

All adverse events (as required by this protocol) must be reported in the source documentation and CRFs with appropriate information, including severity and rating of causality to the study drug/treatment. Adequate source documentation must be available to characterize the severity, duration and causality of each reported adverse event. For purposes of this protocol, The adverse event-reporting period will begin immediately following initiation of treatment, with the adjuvant treatment with TMZ and the Optune device, and end at least 30-days following last study treatment (Pembrolizumab dose, Temozolomide dose, or wearing Optune, whichever comes last). Any SAEs will be followed until stabilization.

9.15 Unanticipated Adverse Device Effect Event (UADE) Reporting

Any potential unanticipated adverse device effect (UADE) will be reported to the local IRB and DISC per local reporting policy and FDA, as applicable.

9.16 Eliciting Adverse Event Information

The investigator is to report all directly observed adverse events and all adverse events spontaneously reported by the trial patient using concise medical terminology. In addition, each trial patient will be questioned about adverse events at each clinic visit following initiation of treatment.

9.17 Adverse Event Reporting Period

The adverse event-reporting period will begin immediately following initiation of treatment, with the adjuvant treatment with TMZ and the Optune device, and end at least 30-days following last study treatment (Pembrolizumab dose, Temozolomide dose, or wearing Optune, whichever comes last). All adverse events that occur in trial patients during the adverse event reporting period must be reported on the CRFs, whether or not the event is considered study treatment-related. In addition, any known untoward event that occurs beyond the adverse event-reporting period that the investigator assesses as possibly related to the investigational medication/product should also be reported as an adverse event.

9.18 Follow-up of Unresolved Adverse Events

Adverse events will be tracked for 30 days following the last study treatment (Pembrolizumab dose, Temozolomide dose, or wearing Optune, whichever comes last). Events continuing at that time will be notes as such.

9.19 Adverse Event Reporting

All serious and unexpected adverse drug reactions must be reported to Merck Global Safety (if attributable to pembrolizumab) and FDA (as applicable). Serious adverse events will be reported to the IRB and DISC per local policy. Serious, unexpected and related SAEs will be tracked for 90 days after last following last study treatment (Pembrolizumab dose, Temozolomide dose, or wearing Optune, whichever comes last).

10. STATISTICAL CONSIDERATIONS:

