6.4 Follow-Up Evaluations During The 12 Cycles of Adjuvant TMZ

All patients will be seen before Cycle 1 of TMZ, before starting the pembrolizumab, and every 3 weeks (+/-4 days) before each subsequent pembrolizumab dose at an outpatient clinic until they complete all 12 cycles of adjuvant TMZ or discontinue TMZ due to toxicity or first progression. Optune compliance reports will be collected remotely or in the clinic setting approximately every 4 (+/- 1) weeks. Contiguous data will be sufficient for Optune compliance reporting, per SOC for the Optune Device.

At each visit the following will be performed except otherwise specified:

- Physical exam and performance status (KPS)
- Blood exams
 - o CBC with differential within 3 days prior to starting each cycle of temozolomide
 - Complete Metabolic Panel prior to each cycle of pembrolizumab and prior to starting each cycle of temozolomide (+/- 7 days)
 - o PT/PTT, INR for patients receiving relevant anti-coagulants
 - o TSH, Free T4 prior to the first infusion of pembrolizumab and then prior to every other pembrolizumab infusion thereafter
- Study lab as specified
- Steroid dose
- Concomitant Medications
- Record of Adverse Events
- TTF compliance report (only every 4 +/- 1 weeks)

An MRI will be performed every 2 months (+/- 7 days) following the baseline MRI until second progression (when study treatment will be terminated). In the case of clinical progression an unscheduled MRI will be obtained within 1 week of the investigator becoming aware of the clinical progression. Contrast agent type and dose will be kept constant for each patient between scans. Disease will be assessed as per iRANO criteria [64] [65] with allowance for potential immune mediated effects at first appearance. No additional MRIs will be required by the study after second progression. Medical follow-up will continue for 30 (+/- 7) days after treatment termination in

order to capture treatment related toxicities. After this visit, mortality will be assessed based on telephone interviews with the patients or the patients' caregivers every 3 months.

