6.6 Post Treatment Evaluations

Treatment will continue according to the protocol until toxicity, second progression or 24 months (the earlier of the three). After treatment termination the patient will be followed every three months via phone call or collected from clinic notes for survival follow up until death or for 5 years, whichever occurs first.

Subjects will be evaluable for survival analysis if they have received Optune treatment, AND have received at least one dose of pembrolizumab, AND have received adjuvant temozolomide. Subjects that are not evaluable for survival analysis will be replaced.

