8.2 Potential Adverse Events: Pembrolizumah

AEs associated with pembrolizumab exposure may represent an immunologic etiology. These immune-related AEs (irAEs) may occur shortly after the first dose or several months after the last dose of pembrolizumab treatment and may affect more than on body system simultaneously. Therefore, early recognition and initiation of treatment is critical to reduce complications. Based on existing clinical study data, most irAEs were reversible and could be managed with interruptions of pembrolizumab, administration of corticosteroids and/or other supportive care. For suspected irAEs, ensure adequate evaluation to confirm etiology or exclude other causes. Additional procedures or tests such as bronchoscopy, endoscopy, skin biopsy may be included as part of the evaluation. Based on the severity of irAEs, withhold or permanently discontinue pembrolizumab and administer corticosteroids. Dose modification and toxicity management guidelines for irAEs associated with pembrolizumab are provided in the Table 3 below.

b: TMZ is to be discontinued if dose reduction to <100 mg/m2 is required or if the same Grade 3 non-hematological toxicity (except for alopecia, nausea, vomiting) recurs after dose reduction.

TMZ = temozolomide; CTC = Common Toxicity Criteria.

Table 3: Pembrolizumab Dose Reduction or Discontinuation

General instructions:

- 1. Corticosteroid taper should be initiated upon AE improving to Grade 1 or less and continue to taper over at least 4 weeks.
- 2. For situations where pembrolizumab has been withheld, pembrolizumab can be resumed after AE has been reduced to Grade 1 or 0 and corticosteroid has been tapered. Pembrolizumab should be permanently discontinued if AE does not resolve within 12 weeks of last dose or corticosteroids cannot be reduced to ≤10 mg prednisone or equivalent per day within 12 weeks.
- **3.** For severe and life-threatening irAEs, IV corticosteroid should be initiated first followed by oral steroid. Other immunosuppressive treatment should be initiated if irAEs cannot be controlled by corticosteroids.

Immune-related AEs	Toxicity grade or conditions (CTCAEv4.0)	Action taken to pembrolizumab	irAE management with corticosteroid and/or other therapies	Monitor and follow-up
Pneumonitis	Grade 2	Withhold	Administer corticosteroids (initial dose of 1-2 mg/kg prednisone or equivalent) followed by taper	 Monitor participants for signs and symptoms of pneumonitis Evaluate participants with suspected

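### The 90-day safety window in section 9.19 leaves out known immune-related events, although section 8.2 says they may appear months after the last pembrolizumab dose

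*Combined protocol and SAP*

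**What the plan says.** On timing of risk, section 8.2 says that irAEs "may occur shortly after the first dose or several months after the last dose of pembrolizumab treatment".

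On collection and follow-up, the protocol has several rules:

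- Sections 9.14 and 9.17 and footnote 16 of the study calendar end the reporting period no earlier than 30 days after the last of pembrolizumab, temozolomide or Optune. Section 9.17 adds that later events that become known, and that the investigator considers possibly related, should also be reported.
- Section 9.18: "Adverse events will be tracked for 30 days following the last study treatment". Events still ongoing then are only noted as continuing.
- Section 9.19: "Serious, unexpected and related SAEs will be tracked for 90 days after last following last study treatment".
- Section 9.14: "Any SAEs will be followed until stabilization".

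On contact with the patient, section 6.4 says: "Medical follow-up will continue for 30 (+/- 7) days after treatment termination". From then on, section 6.4 provides for mortality checks only. Section 6.6 describes contact "every three months via phone call or collected from clinic notes for survival follow up". Section 9.16 has patients asked about adverse events at every clinic visit once treatment has begun, and section 7.1.1 leaves clinic visits after treatment to standard care.

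**The concern.** The extra 60 days of safety follow-up are granted only to events that are serious, unexpected and related. Expectedness is a sensible criterion for deciding what needs expedited reporting. As a criterion for what is collected, it works against its purpose: the better established a late immune toxicity is, the less likely it is to qualify. Section 8.2 names this class of event as one that can appear late.

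Toxicity and tolerability is the first secondary objective (section 3.2), analysed in section 10.2 as proportions with 95% confidence intervals. At stake are the completeness of those proportions and the chance that a delayed serious irAE reaches the study record.

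**Working it through.** The plan has no calculation on this point to reproduce, so the main check is to set the windows side by side.

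| Rule | Events covered | Length | Clock starts |
|---|---|---|---|
| 9.14, 9.17, calendar note 16 | all adverse events | at least 30 days | last of the three treatments |
| 9.18 | all adverse events | 30 days | last of the three treatments |
| 9.19 | serious, unexpected and related SAEs | 90 days | last of the three treatments |
| 9.14 | SAEs already reported | until stabilization | not applicable |
| 9.17, last sentence | known, possibly related events | no limit | no visit or question attached |
| 6.4 | toxicity visit | 30 (+/- 7) days | treatment termination |
| 8.2 | stated latency of irAEs | several months | last pembrolizumab dose |

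**Step 1, the filter.** Section 9.11.3 calls an event unexpected when its specificity or severity does not match the investigator brochure or other risk information. Table 3 manages pneumonitis, colitis, hepatic events, hypophysitis, nephritis and others as recognised pembrolizumab toxicities. A late serious colitis of described severity would then most naturally be classed as expected, and would not enter the 90-day window. A known irAE of unexpected severity would enter it.

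**Step 2, the gap.** 90 - 30 = 60 days in which expected irAEs, serious or not, need not be collected. After day 90 no adverse event window is required.

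**Step 3, when it bites.** The latency in section 8.2 runs from the last pembrolizumab dose; the collection clock runs from the last of three treatments. Under section 6, pembrolizumab may stop at first progression while Optune goes on to second progression or 2 years, and such a patient stays under full collection. The gap matters mainly when the treatments end close together, for example at 24 months or on stopping for toxicity.

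**Step 4, scale.** With the planned 24 patients, one missed patient changes a proportion by 1/24 = 4.2 percentage points. Exact (Clopper-Pearson) 95% intervals, chosen here because section 10.2 names no method:

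- 0/24 = 0% (0 to 14.2%; upper limit 1 - 0.025^(1/24))
- 1/24 = 4.2% (0.1 to 21.1%)
- 2/24 = 8.3% (1.0 to 27.0%)

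**Step 5, how often.** The documents give no late-irAE rate. If the chance per patient were 2%, 5% or 10% (assumed), the chance of at least one among 24, 1 - (1 - p)^24, would be 38%, 71% or 92%. These are chances that such an event occurs, not that it is missed.

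**The case against.** The strongest reply is that late events are not shut out. Section 9.16 puts no end date on asking about adverse events at clinic visits, and section 7.1.1 expects standard-care visits after treatment. Section 9.17 sets a minimum rather than a stop, and asks for later possibly related events to be reported once known. Survival follow-up may itself draw on clinic notes. The calendar also appears to list an adverse event assessment under post-pembrolizumab follow-up without the footnote that carries the 30-day end, although column alignment in the extracted table is uncertain and no duration is given. All of this stands. A reader might infer that late irAEs go unreported, or that patients are never asked about them; the documents do not support that. What remains is that no required collection window covers these events after day 30, so their capture depends on visits whose timing the protocol does not set.

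Three further limits apply. The investigator brochure is not among the documents and Table 3 is not the expectedness reference, so the classification in step 1 is likely, not certain. The 12-week limit in Table 3 might be read as a follow-up horizon that outlasts day 30, but it is a rule on discontinuing pembrolizumab and says nothing about how long events are collected. Sections 9.14 and 9.18 might be read as a flat contradiction; they can also be read as a specific rule for SAEs beside a general rule for adverse events, so they need a clarifying sentence.

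**Conclusion.** The point holds as a gap in required collection. Section 8.2 places irAEs months after the last pembrolizumab dose, general collection may end at day 30, and the one window that runs to day 90 carries a condition that tends to exclude known irAEs of known severity. The likely effect is under-ascertainment of late irAEs in the toxicity proportions, mainly in patients whose treatments end close together.

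The size is 4.2 percentage points per missed patient with n = 24. The total cannot be estimated, because neither the late-irAE rate nor the share found through standard care is given. It would go too far to infer that a comparison is biased in favour of the combination: section 10.2 plans toxicity as a single-arm description without a comparator, so the harm is an incomplete count. The primary PFS test is not affected. The change is worth making because it is cheap and concerns the first secondary objective. The conclusion assumes that the brochure lists the recognised irAEs at the severities at which they would appear.

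**What to change.** 1. In section 9.19, remove the condition that the event be unexpected. State that all SAEs and all suspected irAEs, regardless of expectedness, are collected for 90 days after the last study treatment. Say explicitly that this covers new onsets, since the present verb could be read as following events already reported. Align section 9.17 and calendar note 16.
2. Keep the clock on the last study treatment. Counting from the last pembrolizumab dose would shorten present cover: if pembrolizumab ended at month 8 and Optune at month 20 (an illustration), 90 days would run to about month 11 instead of about month 23.
3. Add one SAE/irAE check, by phone or from clinic notes, to the first 3-monthly survival contact. Counted from treatment termination (section 6.6), this falls at about day 90. The calendar allows +/- 1 month, so state that this check is made on or after day 90.
4. State that section 9.14 governs ongoing SAEs, which are followed until stabilization, and that the 30-day stop in section 9.18 applies to other adverse events.

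The cost is a wording amendment, one question or chart check per patient, and a few more adverse event records. Reported toxicity may rise slightly. No visit is added, and no dose, treatment or stopping rule changes.

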10.1 Primary Endpoint

Our primary endpoint is progression-free survival time from enrollment to progression or death or censoring, whichever occurs first, with the goal of determining whether the triple combination treatment increases PFS in newly diagnosed GBM patients when compared to TTFields+TMZ historical control patients from the EF-14 study. We will use one-sample log-rank test to compare PFS between the triple combination arm relative to the historical control arm.

10.2 Secondary endpoints

We are proposing 3 secondary endpoints:

- 1. Toxicity and tolerability of the triple combination treatment in newly diagnosed GBM patients.
- 2. Overall survival time from enrollment to death or censoring, whichever occurs first() and radiographic response (RR) at 6, 12, 18 and 24 months of the triple combination in newly

diagnosed GBM, as compared to the historical control arm.

3. Augmentation of TTFields-initiated glioma-specific immune reaction by pembrolizumab.

We will estimate proportions and 95% confidence intervals for patients in the triple combination arm who experience toxicities and other types of AEs and SAEs. We will use the log-rank test to compare OS between the triple combination arm relative to the historical control arm. We will use one-sample proportion test to compare RR between the triple combination arm and historical control arm. We will use mixed effect regression to assess changes in response variables related to glioma-specific immune reaction before, during, and after treatment with pembrolizumab.

10.3 Sample Size Considerations

To determine if the proposed sample size of 24 patients enrolled in the triple combination arm will allow us to detect a clinically relevant improvement in median PFS relative to the median PFS of 6.7 months observed in the historical control arm, we assumed an accrual period of 12 months, an accrual rate of 2 patients per month, an additional 18 months of follow-up after the end of accrual, and proportional hazards. After confirming that the Weibull distribution could reasonably be used to characterize PFS times in the historical control arm, we estimated the Weibull shape parameter k from the historical control PFS curve. The shape parameter k determines if the hazard rate underlying a survival curve is accelerating over time (k>1), constant over time (k=1; identical to exponential survival), or decelerating over time (k<1). Based on a shape parameter estimate of k=0.88 with empirical 95% confidence interval (0.82,0.95) obtained via simulation of the historical control data, our proposed sample size of 24 patients in the triple combination arm should allow us to detect in improvement in PFS of 6 to 8 months with 80% power and a 1-sided significance level of 0.05 (detectable effect size methodology from Wu and Xiong, 2014 [69]).

10.4 Data Analysis Considerations (Protocol v10.1)

[name], sub-Investigator at USC, will assist with secondary analysis of coded clinical data for primary and secondary endpoints. A coded limited data set will be shared for purposes of data analysis and a data use agreement (DUA) will be included as part of the statement of work. Data will be stored in UF Box and [name] and his designee will be provided access via UF institutional procedures. The LDS will be transferred to USC and will be stored on secure, duallyauthenticated USC servers with limited access only to [name] and his designees. Analyzed data files will also be password protected and stored on password protected computers.

Additionally, [name] will perform correlative studies which include expression analysis of peripheral blood mononuclear cells (PBMCs) and tumor samples to determine if correlations in expression of key gene pathways with the clinical outcome of enrolled subjects with newly diagnosed GBM receiving the study treatment of adjuvant temozolomide + TTFields + pembrolizumab. PBMCs and tumor samples will include the subject's study ID, sample type and timepoint and date of collection. A corresponding coded limited data set that includes subject ID, dates associated with the individual, clinical data/survival data, treatment history and detailed response data will be shared with [name] in order to accurately identify and characterize signatures of response. We will treat survival in the 2THETOP data as a continuous variable and

develop computational models that incorporate all key clinical and molecular characteristics to define response signatures that are also continuous with correlation with survival. We plan to apply novel computational bioinformatics to identify cytotoxic T lymphocyte (CTL) clones that are shared between the tumor microenvironment (TME) and the periphery prior to treatment and at the time of radiographic changes and between pathologically proven immune changes and true recurrence. The goal is to identify T cell clones that were expanded after treatment and capable of infiltrating the TME to induce productive anti-tumor immunity. This information will help determine if immune resistance is a function of changing of the "guards" or changing in the TME's immunosuppressive functions. Each TCR clone will be paired with its expression profile to allow for the identification of the master regulatory subnetwork specific in these TME access-enabled tumor-specific CTL clones as compared to those that were expanded in the periphery but failed to reach the TME. Next, we plan to answer the following questions: 1) What defines the systemic signal created by study treatment? 2) What systemic signals distinguish objective responders from non-responders? and 3) What systemic signals may prevent non-responders from responding? For example, in certain non-responders, is it because their immune system also activates an alternate immune checkpoint (e.g., LAG3, CTLA4, IDO1, TGIT etc.) in addition to PD-1/PD-L1? and if so, will using a combination of checkpoint inhibitors be more effective? The answers to these questions will help us develop a more robust signature that can predict response and guide subsequent TTFields-based combination therapy. Clinical data will be stored in UF Box and [name] and his designee will be provided access via UF institutional procedures. Sequencing data will be raw RNAseq and DNA sequences in FASTQ format. The raw sequencing data from all correlative studies for 2THETOP are stored in UF HiPerGator. UF will initiate the transfer to USC using Globus (which is a highly secure and fast transfer system frequently used in high data content transfer). Sequencing and associated clinical data will be stored on secure dually-authenticated USC supercomputer and servers with limited access to only [name] and his designees. Analyzed data files will also be password protected and stored on password protected computers.

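### Section 10.4 treats survival as a plain continuous variable and gives no place to censored times; the loss depends on a data cut-off that the section does not state

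*Combined protocol and SAP*

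**What the plan says.** Section 10.4 is the only place that describes how survival enters the signature analysis. The sentence begins "We will treat survival in the 2THETOP data as a continuous variable and" and goes on to "develop computational models that incorporate all key clinical and molecular characteristics to define response signatures that are also continuous with correlation with survival". It names no estimator, no rule for patients alive at analysis and no data cut-off, and it does not say whether survival means OS or PFS.

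Section 10.2 is explicit about censoring. It defines OS as "Overall survival time from enrollment to death or censoring, whichever occurs first", and its test is a censored-data method: "We will use the log-rank test to compare OS between the triple combination arm relative to the historical control arm".

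The design figures in section 10.3 are "the proposed sample size of 24 patients enrolled in the triple combination arm"; "we assumed an accrual period of 12 months, an accrual rate of 2 patients per month"; and "an additional 18 months of follow-up after the end of accrual, and proportional hazards". Those follow-up figures belong to the PFS sample-size calculation. Section 6.6 and footnote 14 of the study calendar provide for survival follow-up every 3 months until death or for 5 years.

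**The concern.** A correlation with a continuous variable needs a completed value for every patient. A patient alive at cut-off has none. An analyst who follows 10.4 as written has two options:

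- **Take observed times at face value.** A patient censored at 20 months then counts the same as one who died at 20 months.
- **Use deaths only.** This removes the longest survivors, who are the patients a response signature most needs.

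Both weaken true associations. Section 10.4 intends the signature to predict response and to steer later TTFields combinations. With 24 patients there is little power to give away when pathways are being selected.

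**Working it through.** **1. The plan's own figure.** The documents give no censoring percentage for survival. The nearest figure is the detectable PFS improvement of 6 to 8 months in section 10.3, which checks the accrual and follow-up inputs used below.

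Model: one-sample log-rank test under a Weibull model with proportional hazards, n = 24, control median 6.7 months, uniform accrual over 12 months plus 18 months of follow-up, one-sided 0.05.

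Power = Φ{[√n(p0 − p1)/√p0 − 1.645]·√p0/√v}, where, under the alternative, p1 is the event probability, p0 the mean null cumulative hazard at the observed time, and v the variance of (event indicator − null cumulative hazard).

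Solving for 80% power gives improvements of 7.6, 6.7 and 5.9 months at k = 0.82, 0.88 and 0.95. The plan's 6 to 8 months reproduces.

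**2. Censored share of OS at that follow-up.** Uniform accrual over 12 months plus 18 months gives potential follow-up of 18 to 30 months. Assumptions: exponential OS with median m, administrative censoring only.

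Censored share = (m/ln 2)/12 × (2^(−18/m) − 2^(−30/m))

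| OS median | Calculation | Censored |
|---|---|---|
| 20.9 (EF-14 final, section 2.1) | 2.513 × (0.5505 − 0.3697) | 45% |
| 16 (TMZ alone, section 2.1) | 1.924 × (0.4585 − 0.2726) | 36% |
| 27 (assumed improvement) | 3.246 × (0.6300 − 0.4629) | 54% |

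The Weibull shape matters little: at a median of 20.9, k = 0.88 gives 46% and k = 1.2 gives 44-45%. A Weibull through 20.9 months and the 43% alive at 2 years in section 2.5 gives 43%. Expected deaths at 45% censoring: 24 × (1 − 0.454) = 13.1.

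**3. Dependence on timing.** Same model, OS medians 20.9 to 30 months:

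| Time of analysis | Censored |
|---|---|
| 12 months after last enrolment | 55-66% |
| 24 months after last enrolment | 37-50% |
| 36 months after last enrolment | 25-38% |
| 60 months after last enrolment | 11-22% |
| 60 months per patient | 14-25% |
| 84 months per patient (24 on treatment + 5 years) | 6-14% |

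**4. Effect on a true association.** n = 24, 18-30 months of follow-up, one normally distributed marker, HR 1.65 per SD (log-HR 0.5), two-sided 5% test. Two separate simulations:

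| Method | Weibull k = 1.2, 44% censored | Exponential, 45% censored |
|---|---|---|
| Complete times, rank correlation | – | 0.43 |
| Cox score test | 0.40 | 0.37 |
| Rank correlation, observed times | 0.30 | 0.28 |
| Rank correlation, deaths only | 0.07-0.11 across scenarios | 0.08 |
| Mean correlation, complete to observed times (absolute) | 0.37 to 0.30 | 0.36 to 0.29 |

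Rough check on the Cox row: 0.5 × √13.1 = 1.81, and Φ(1.81 − 1.96) = 0.44. This large-sample value is a little above the simulated 0.37-0.40, as expected with so few deaths. For HR 2.0 per SD, power is 0.65 with Cox against 0.50 with observed times.

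At 14% censoring, the mean correlation on observed times moves only from 0.37 to 0.36.

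**5. False positives.** For a null marker unrelated to entry date, the false-positive rate on observed times stays at about 5%. If the marker correlates with entry date at 0.5, 0.7 or 0.9, it becomes 9%, 13% or 20%, against 5-6% with Cox. The mechanism is that later entry caps the observed time, so entry date predicts observed time even when it does not predict survival.

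**The case against.** The strongest reply is that 10.4 names no estimator. A Cox model also treats time as continuous, and the phrase "define response signatures that are also continuous with correlation with survival" sits in a section that also contrasts responders with non-responders. So continuous may mean only not dichotomised. The shared data set includes dates and survival data, which would support a censored analysis. This stands in part: a reader might infer that the plan will ignore censoring, but the documents are silent on it and do not say so. The objection does not remove the point, because the words written describe a method with no place for a censored time.

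A reader might also infer that a third to a half of the times will be censored whatever happens. That does not follow. The 18 months is an assumption of the PFS calculation, not a cut-off for this analysis, and the planned 5-year survival follow-up brings censoring to about 6-25%. Equally, 10.4 does not commit to waiting for it.

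A third tempting inference is that the method creates spurious signatures. Censoring alone does not. A marker tied to entry date, for example through assay batch, would be needed, and no section shows one.

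Finally, the simulations test one marker, whereas 10.4 plans multivariable models. They show direction and rough size, not the power of the planned analysis. Even Cox power is low at this sample size.

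**Conclusion.** The point holds as a mismatch between the literal method in 10.4 and the censored definition of OS in 10.2. At an analysis about 18 months after last enrolment, taking observed times at face value costs about 9 to 10 percentage points of power for a marker with HR 1.65 per SD (0.37 to 0.28, or 0.40 to 0.30). Using deaths only leaves power at about 0.1. At a late cut-off the attenuation from using observed times is small; discarding survivors would still remove the longest survivors.

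These figures assume uniform accrual, no loss to follow-up, exponential or mildly non-exponential OS around the EF-14 median, and proportional hazards, which favours Cox. False-positive inflation is a conditional risk only.

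The consequence is limited. The signature is not among the objectives listed in section 3, and neither the primary PFS comparison nor the OS test in 10.2 is affected. It is a worthwhile improvement rather than a necessary correction.

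**What to change.** In 10.4, replace the wording that makes survival a continuous variable with a statement along these lines: OS will be analysed as a time-to-event outcome (time plus death/censoring indicator), for example by Cox regression for marker association and a censoring-aware concordance measure for signature performance; neither survival nor the signature score will be dichotomised. Add the data cut-off for this analysis.

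The cost is a sentence or two, with no new data, since dates and survival status are already in the shared data set. One caution applies: with about 13 deaths at an early cut-off, a multi-gene penalised Cox model would be unstable. The choice of model can therefore stay open, provided that it handles censoring.
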